9.6 Examination of subgroups

Data for the primary efficacy endpoint will also be presented for key, pre-defined subgroups of patients. Concomitant use of glucocorticoids will be one key subgroup as earlier studies have suggested that it may have effect on the study treatment. As CD73 response (and IL-6 and HIF-1 α) may be also genetically determined/individual, another key subgroups will be CD73 responder status (determined by a 2-fold elevation in CD 73 (from baseline to peak value)). In addition, if analyses indicate yet another, but currently unknown but relevant subgroups, they will be analysed as separate subgroup analyses for exploratory purposes

Key subgroups included in analyses

- Concomitant use of glucocorticoids
- CD 73 responder status (responders vs. non-responders)
- IL-6 responder status
- HIF-1 α responder status

10 Demographic and other baseline characteristics

Number of patients enrolled into the study at screening and the reasons for screening failures will be summarized. The number of patients entering and completing the study will be summarized. All patients discontinuing the study will be summarized together with the reason(s) for discontinuation.

Demographic and baseline characteristics will be summarized by treatment using descriptive statistics. Following variables will be analysed.

- Gender
- Age at entry
- Race
- Height
- Weight
 - If actual weight is not available for a patient, then predicted body weight will be used in its place
 - Predicted body weight (kg) is calculated using the following formulae:
 - Males: $50 + 0.91(\text{height in cm} - 152.4)$
 - Females: $45.5 + 0.91(\text{height in cm} - 152.4)$
- Major surgical outcomes affecting patient
 - Open abdomen (yes/no)
 - Left renal vein ligated (yes/no)
 - Clamping time above the renal arteries
- Medical history
- Concomitant medications/therapies
- Pregnancy test (females of child bearing potential).

Similarly, the duration of the surgical procedure and peri procedural information will be summarized by treatment. Additional concomitant procedures will be listed only.

Medical history and concomitant medications/therapies will be presented only by frequency and subject count-based tables according to WHO Anatomical Therapeutic Chemical (ATC) classification.

Pregnancy test results (females of child-bearing potential) will be presented only descriptively by a subject count-based table.

11 Extent of exposure and compliance

Treatment exposure, study duration and treatment compliance will be summarised by treatment groups using descriptive statistics.

12 Analysis of efficacy

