Even in elective non-emergency AAA repair, patients experience a SIRS due to clamping and unclamping of the aorta (Bown et al. 2001). Compared to patients undergoing endovascular repair for a ruptured aneurysm patients undergoing open repair are considered to suffer from a two-fold SIRS strain due to the initial rupture and then the open surgery involving clamping and un-clamping of the aorta (Makar et al. 2013). In addition, preliminary human data has shown that cross-clamping the infra-renal aorta is associated with decreased CD73 activity in post-operative serum samples, which implies that hypoxia and CD73 mediated compensatory mechanisms are impaired or adapt too slowly to the ischemic insult (Jalkanen et al. 2016). This

implies that any drug substance that could enhance the natural response to hypoxia by increasing CD73 activity mediated adenosine production, could be beneficial against hypoxia-induced inflammation and increased capillary leakage (Eltzschig et al. 2012). It has been well established that CD73 expression and its ecto-5'-nucleotidase activity can be induced by IFN beta in cultured endothelial cells with a consequent decrease in vascular permeability (Niemelä et al. 2004). IFN beta-1a has already been demonstrated as safe and effective in the treatment of ARDS patients in the FPCLI001 study, with a similar underlying pathological molecular mechanism (Bellingan et al. 2014). Thus, FP-1201-lyo offers a promising treatment for CD73 and adenosine regulated post-ischemic injury not in one but several organs under risk during operative treatment of RAAA.

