1.3 Mechanism of Action

CD73 is an ecto-5'-nucleotidase enzyme expressed on vascular endothelium, epithelial cells and on a subset of leukocytes (Zimmermann et al. 1992). Through dephosphorylation of adenosine monophosphate (AMP), it yields adenosine, a potent anti-inflammatory molecule, which prevents vascular leakage and inhibits leukocyte recruitment into sites of inflammation (Colgan et al. 2006). Such endogenous protective mechanisms are enhanced in the presence of hypoxia (Thompson et al. 2004). CD73 expression on immune and vascular cells and extracellular adenosine production have been linked to the alleviation of ischemia-reperfusion injury of the myocardium, intestine and kidneys in preclinical settings.

Preclinical studies have shown that CD73 expression is up-regulated in the endothelium by IFN beta-1a treatment in a time and dose dependent fashion (Niemelä et al. 2004). Also, in a mouse model of MOF, IFN beta was shown to be of benefit in protecting the alveolar structure from damage when compared to vehicle treated controls (Kiss et al. 2007). In addition, IFN beta treatment has been shown to prevent vascular leakage in ALI animal models. Enhanced adenosine production also inhibits leukocyte infiltration, thus reducing the escalation of inflammation and reperfusion

injury (Koszalka et al. 2004, Lennon et al. 1998 and Volmer et al. 2006). In a recent study, IFN beta-1a therapy was shown to reduce mortality in patients with ARDS by over 80 % (Bellingan et al. 2014). Pre-clinical data suggests that according the mechanism of action, FP-1201-lyo could also be protective in the reperfusion injury of the myocardium (Eckle et al. 2007), intestine (Hart et al. 2011) and kidneys (Grenz et al. 2008) and against SIRS induced by hypoxia (Eltzschig et al. 2012).

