6.6 Exploratory Variables

6.6.1 *Methods and Timing for Assessing, Recording and Analysing Pharmacodynamic Parameters*

Blood samples for the NAb assessments are collected at D0 pre-dose (baseline) and at D30. Blood samples for the MxA, Tentative Disease Specific Marker (CD73) and Potential Inflammatory Markers (IL-6 and HGF) assessments are collected at D0 pre-dose (baseline), at D1, D2, D3, D4, D5, D6, D9 and D13 assuming the patient is hospitalized as detailed in the study flow charts in Tables 5 and 6.

MxA, CD73, NAb and PIM blood sample preparation and sample storage details are provided in the study specific Laboratory Manual. It is essential that the actual time and date of collection of each PD sample be recorded in the sample collection form provided with the laboratory kits.

MxA, CD73 and NAb samples are analysed centrally by [REDACTED], and PIMs in [REDACTED].

The total volume of blood required for samples per patient is shown below in Table 4.

Table 4 Total Volume of Blood required for MxA, CD73 and PIMs

PD Parameter	Number of Samples	Per Sample Volume (mL)	Total Volume (mL)
CD73	9	2.5	22.5
MxA	9	2	18
PIM	9	2.5	22.5
NAb	2	2.5	5

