8.5 Evaluation of efficacy

8.5.1 *Evaluation of primary efficacy endpoint*

The primary endpoint of the study will be:

- All-cause mortality at D30

To be eligible for efficacy analysis each patient must receive at least two doses of the study medication with an effect time of 12 hours after second dose. This means that a death within 36 hours from the first dose of study treatment leads to exclusion from efficacy analysis. This derives from the fact that based on the prior clinical phase I/II studies with interferon beta-1a, its effect on the expression of CD73 and production of adenosine will require 12 to 24 hours from administration of the drug. Thus, therapeutic levels will not be reached until 12 hours from the second dose, i.e. 36 hours from the first dose. Measuring efficacy against multi-organ failure prior to this point is misleading because therapeutic levels have not yet been reached.

The efficacy analyses will be conducted using logistic regression model for the observed mortality rates in the two treatment groups. Stratification factors used in the randomisation will be included in the model. Primary result will be presented as an adjusted odds ratio and a 95% CI for the adjusted odds ratio. Also, a 95% confidence interval (CI) for the difference in the observed mortality rates will be calculated. A two-sided significance level of 0.05 will be used for all analyses.

There will additionally be an evaluation of the homogeneity of the treatment effect by investigating treatment by centre and treatment by baseline factor interactions in the logistic model. Data for the primary efficacy endpoint will also be presented for key, pre-defined subgroups of patients together with 95% CIs for the difference in those rates to supplement the investigation of homogeneity. Mortality at D30 will be illustrated also using survival function and Kaplan-Meier curves including log-rank test as an exploratory analysis.

8.5.2 *Evaluation of secondary efficacy endpoints*

By way of further confirmatory measures of efficacy, the following endpoints will be analysed:

- Time and reason/diagnosis of death up to D90 (3 months)
- Number of VFDs up to D30
- Number of days receiving hemodialysis at D30 and D90
- Number of ICU free days up to D30
- Organ failure free days up to D30
- Neutralizing antibodies IFN beta (NAbs) in whole blood samples up to D30
- Number of days in hospital up to D30 and D90 (length of stay in another health care facility)

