Table 14.2.1.11.3	Length of stay in another health care facility up to D30 excluding deaths (FAS-E)
Table 14.2.1.11.4	Length of stay in another health care facility up to D30 excluding deaths (PPS)
Table 14.2.1.12.1	IAP values by timepoint (FAS-E)
Table 14.2.1.12.2	IAP values by timepoint (PPS)
Table 14.2.1.12.3	IAP values by timepoint excluding early deaths (FAS-E)
Table 14.2.1.12.4	IAP values by timepoint excluding early deaths (PPS)
Table 14.2.1.13.1	IAP grades by timepoint (FAS-E)
Table 14.2.1.13.2	IAP grades by timepoint (PPS)
Table 14.2.1.13.3	IAP grades by timepoint excluding early deaths (FAS-E)
Table 14.2.1.13.4	IAP grades by timepoint excluding early deaths (PPS)
Table 14.2.1.14.1	Disability on D90 measured with mRS (FAS-E)
Table 14.2.1.14.2	Disability on D90 measured with mRS (PPS)
Table 14.2.1.14.1	Neutralizing antibodies (FAS-E)
Table 14.2.1.14.2	Neutralizing antibodies (PPS)
	Pharmacodynamics
Table 14.2.2.1.1	MxA concentration (FAS-E)
Table 14.2.2.1.2	MxA concentration (PPS)
Table 14.2.2.2.1	MxA ANOVA (FAS-E)
Table 14.2.2.2.2	MxA ANOVA (PPS)
Table 14.2.2.3.1	CD73 concentration (FAS-E)
Table 14.2.2.3.2	CD73 concentration (PPS)
Table 14.2.2.4.1	CD73 ANOVA (FAS-E)
Table 14.2.2.4.2	CD73 ANOVA (PPS)
Table 14.2.2.5.1	Potential inflammatory markers (FAS-E)
Table 14.2.2.5.2	Potential inflammatory markers (PPS)
Table 14.2.2.6.1	PIM ANOVA (FAS-E)
Table 14.2.2.6.2	PIM ANOVA (PPS)
	Subgroup analyses
Table 14.2.1.1.1	All-cause mortality D30 by subgroups
Table 14.2.1.2.1	Logistic regression of All-cause mortality D30 by subgroups
	Safety Tables
Table 14.3.1	Extent of exposure and compliance (FAS-S)
Table 14.3.2	Summary of TEAEs (FAS-S)
Table 14.3.3.1	Treatment emergent adverse events (FAS-S)
Table 14.3.3.2	TEAEs by causality (FAS-S)
Table 14.3.3.3	TEAEs by severity (FAS-S)
Table 14.3.3.4	TEAEs by maximum severity (FAS-S)
Table 14.3.3.5	TEAEs by causality and severity (FAS-S)
Table 14.3.3.6	TEAEs by causality and maximum severity (FAS-S)
Table 14.3.4.1	TEAEs during treatment period (FAS-S)
Table 14.3.4.2	TEAEs during treatment period by causality (FAS-S)
Table 14.3.4.3	TEAEs during treatment period by severity (FAS-S)

Table 14.3.4.4	TEAEs during treatment period by maximum severity (FAS-S)
Table 14.3.4.5	TEAEs during treatment period by causality and severity (FAS-S)
Table 14.3.4.6	TEAEs during treatment period by causality and maximum severity (FAS-S)
Table 14.3.5.1	TEAEs during short-term follow-up period (FAS-S)

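### CD73 responder status is a post-dose subgroup, so active-versus-placebo mortality comparisons within it are not protected by randomisation

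*SAP*

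**What the plan says.** SAP 9.6 plans to present the primary endpoint in key, pre-specified subgroups. One is introduced as "another key subgroups will be CD73 responder status (determined by a 2-fold elevation in CD 73 (from baseline to peak value", and it appears again in the closing list. Only further subgroups, not yet identified, carry a caveat: "they will be analysed as separate subgroup analyses for exploratory purposes".

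Protocol 8.5.1 says that primary-endpoint data will be "presented for key, pre-defined subgroups of patients together with 95% CIs for the difference in those rates", in support of the check that the treatment effect is homogeneous. The interaction tests in that check concern centre and baseline factors. SAP 19.3 lists a table titled "Logistic regression of All-cause mortality D30 by subgroups".

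On the marker:
- Protocol 1.1 says that CD73 "can be induced by IFN beta in cultured endothelial cells with a consequent decrease in vascular permeability".
- Protocol 1.3 cites preclinical studies in which "CD73 expression is up-regulated in the endothelium by IFN beta-1a treatment in a time and dose dependent fashion".
- Protocol 8.5.1 justifies the 36-hour exclusion from prior clinical phase I/II studies of interferon beta-1a: "its effect on the expression of CD73 and production of adenosine will require 12 to 24 hours from administration of the drug".
- SAP 12.3.1 analyses serum CD73 as an outcome, in a model with treatment, day and their interaction.

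On sampling, Protocol 6.6.1 takes one pre-dose sample and then samples "at D1, D2, D3, D4, D5, D6, D9 and D13 assuming the patient is hospitalized". The footnote to Protocol Table 5 limits assessments before D30 to patients still in the hospital where they were operated on. Protocol 3.2.4 and 6.6.1 follow CD73 to D13; SAP 5 and 12.3.1 stop at D6. SAP 9.2 rules out imputation.

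**The concern.** A subgroup comparison of two randomised arms is fair when membership is fixed before treatment. Responder status is not: it is read from samples taken after dosing, on the marker the drug is meant to raise. If the drug turns some patients into responders who would not have responded on placebo, active responders and placebo responders are differently selected groups. The same holds for non-responders.

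A second route runs through sampling. A patient who dies or leaves the operating hospital early has fewer chances to show a 2-fold rise, so the outcome can help decide the subgroup.

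At stake is interpretation. A mortality difference in CD73 responders, shown as a key subgroup without a caveat, would read as a randomised result and as support for the mechanism. SAP 9.6 suggests that response may be genetic or individual; that rationale would suit a trait measured before dosing, not an observed rise after it.

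**Working it through.** The plan gives no responder rates and no link between response and prognosis, so it has no figure of its own to reproduce. The calculations below use assumed inputs and show how the bias arises; they do not estimate it.

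**1. Shared prognosis, no truncation.** Severity f ~ N(0,1). In both arms logit P(death) = -1.35 + f, which gives 24.4% mortality and no drug effect on death. This is an assumed value between two averages of the planning rates in Protocol 8.2 (15% active, 37% placebo): (2 x 15 + 37)/3 = 22.3% weighted 2:1, and (15 + 37)/2 = 26% unweighted. Response: logit P(response) = -1.5 + d x active - b x f, integrated numerically over f. A positive b means that sicker patients respond less. Differences are taken before rounding.

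Large shift in response (d = 2.5):

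| b | Response, active / placebo | Responder mortality, active v placebo | False difference, points |
|---|---|---|---|
| 0 | 73% / 18% | 24.4% v 24.4% | 0 |
| 0.5 | 72% / 19% | 22.3% v 18.7% | +3.6 |
| 1 | 70% / 22% | 20.2% v 14.8% | +5.3 |
| -0.5 | 72% / 19% | 26.5% v 30.9% | -4.4 |
| -1 | 70% / 22% | 28.2% v 36.0% | -7.7 |

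In non-responders the range is -5.4 to +7.1. With a smaller shift (d = 1.0, response 38-40% v 18-22%) the ranges are -3.3 to +2.0 in responders and -2.1 to +2.3 in non-responders. With no shift (d = 0) the difference is 0 at every b.

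**2. Truncation by death, no shared prognosis.** A simulation of 1.5 million patients assumed 37% mortality in both arms, unrelated to underlying response; deaths only after 36 hours; and one sample a day from D1 to D6 while alive. Log2 fold change had SD 0.6 and mean -0.3 on placebo; a responder has a peak of at least 1.
- Active mean -0.3 (no shift): +0.2 points in responders and 0.0 in non-responders, which is simulation noise.
- Active mean +0.4 (response 59% v 8%): responders 31.5% v 29.7%, or +1.8; non-responders 45.0% v 37.6%, or +7.4.
- Active mean +1.0 (response 95% v 8%): +4.4 and +42.4. The last figure is extreme because the few active non-responders left are mostly early deaths.

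So an underlying response unrelated to prognosis does not remove the bias once treatment shifts CD73.

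**3. Precision.** SAP 8 gives 35 evaluable patients at the first interim; the final number is not stated. A 2:1 split of about 23:12 is assumed. SE = sqrt[m1(1 - m1)/(23 x R1) + m0(1 - m0)/(12 x R0)], where m is responder mortality and R the response rate. For d = 2.5, b = 1: sqrt[0.202 x 0.798/(23 x 0.697) + 0.148 x 0.852/(12 x 0.221)] = 0.240, or 24 points. Over all cases with a shift the range is 24 to 34 points. Expected placebo responders number 12 x 0.18 to 12 x 0.22, about 2 to 3. The chance that none of the placebo patients is a responder who dies, leaving no finite odds ratio, is (1 - R0 x m0)^12 = 37% to 67%.

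The largest bias-to-SE ratio is 7.7/31.5 = 0.24 in responders and 7.1/23.1 = 0.31 in non-responders. At an assumed 50 patients (33:17) the ratios are 0.29 and 0.37.

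**The case against.** The strongest reply is that little depends on this table. The study stopped after the first interim, no success criterion uses the subgroup, noise exceeds every bias in the severity model, and two or three placebo responders could not support a credible claim. All of that stands, and it limits the weight of the point. It does not make the table sound: a comparison that is both unprotected and too imprecise to interpret should not be shown as a key subgroup without a caveat.

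It can also be said that CD73 is already exploratory, since Protocol 3.2.4 and 6.6 place it under that label. This is true of the marker. SAP 9.6 does not carry the label over to this subgroup.

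Third, the within-stratum contrast is partly inferred. SAP 9.6 speaks only of presenting data, the title in SAP 19.3 does not specify a model, and Protocol 8.5.1 never names CD73 responders. The reading comes from taking the three together. It is the natural one, because a homogeneity check compares treatment effects across subgroups.

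Fourth, a reader might infer that the peak has no window at all. That goes too far: the SAP's CD73 variable runs to D6, which is the likely intention. What remains open is that SAP 9.6 does not say so, the protocol runs to D13, and there is no rule for incomplete series.

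**Conclusion.** The point holds as a structural one. Active-versus-placebo comparisons within CD73 strata are not protected by randomisation. They are biased if treatment shifts the observed response and that response is related to death, through shared prognosis or because death or leaving the operating hospital shortens the series. The bias is zero if treatment does not shift the observed response.

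In the severity model, the false difference under a large shift is -7.7 to +5.3 points in responders and -5.4 to +7.1 in non-responders: at most about 0.3 SE and 0.4 SE respectively. Every input is assumed, and truncation can add to these figures, so they are not bounds.

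Three stronger readings are not supported. The trial's main result is not affected: the primary FAS-E analysis does not use responder status. The documents do not show that the drug raises serum CD73 in these patients; they cite cell, preclinical and earlier clinical work on CD73 expression. Nor can the bias be said to favour the drug, since its sign changes with the assumptions.

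The missing thresholds for IL-6 and HIF-1 alpha responders, and the use of HGF in some places and HIF-1 alpha in others, are separate clean-up items and add nothing to the weight of this point.

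**What to change.** In SAP 9.6, define the treatment-effect subgroups by pre-dose variables only, for example baseline CD73, baseline IL-6 and glucocorticoid use before the first dose. Limit the subgroup confidence intervals and the subgroup logistic regression in SAP 19.3 to these.

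Report CD73 responder status, any other post-dose responder status and on-study glucocorticoid use as exploratory and descriptive: counts and deaths by arm, a statement that the comparison is not randomised, and no efficacy claim. State that the peak is taken to D6, or reconcile that with the protocol's D13, and show patients with incomplete series separately.

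The cost is SAP wording and re-programmed subgroup flags. Baseline markers and medication from screening onwards are already collected (Protocol 5.7 and 6.6.1). The price is that baseline strata answer a different question: whether post-dose CD73 response modifies the treatment effect would be described, not tested.

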12.1.1 Primary efficacy variables

Primary efficacy variable is the all-cause mortality at D30. The primary efficacy analysis will be conducted using logistic regression model for the observed mortality rates in the two treatment groups. Stratification factors sex and age used in the randomisation will be included in the model. Primary result will be presented as an adjusted odds ratio and a 95% CI for the adjusted odds ratio. Also, a 95% exact unconditional confidence interval (CI) for the difference in the observed mortality rates will be calculated. As a sensitivity analysis, unadjusted results will also be presented.

For the primary comparison, a p-value less than 0.04664 was planned to be considered as statistically significant due to O'Brien-Fleming alpha spending used for the Interim analyses. Due to the study discontinuation after the first Interim analysis, two-sided significance level of 0.05 will be used for all analyses.

12.2 Secondary efficacy variables

The following secondary endpoints will be analysed:

- Time and reason/diagnosis of death up to D90 (3 months)
- Number of VFDs up to D30
- Number of days receiving hemodialysis at D30*
- Number of ICU free days up to D30*
- Organ failure free days up to D30
- Number of days in hospital up to D30 (length of stay in another health care facility)*
- Prevalence of abdominal compartment syndrome, i.e. intra-abdominal pressure (IAP) value differences between study groups
- Disability on D90 measured by modified ranking scale (mRS)
- Neutralizing (and anti-drug) antibodies IFN beta (ADAs and NAbs) in whole blood samples up to D30

*ICU free days and number of days in hospital, length of stay in another health care facility and number of days receiving hemodialysis at D90 summarized in pharmacoeconomic tables

All-cause mortality at D90 (3 months) will be compared using Cox regression model including stratification factors (if feasible). Estimated hazard ratios will be presented with associated 95% CIs and log-rank p-values for the FAS-E. Also, similar logistic regression as for the primary endpoint (D30 mortality) will be done.

For endpoints number of VFDs, number of ICU free days, organ failure-free days, number of days on hemodialysis, number of days in hospital, length of stay in another health care facility and IAP values, data will be summarised in terms of the mean, median, minimum and maximum, and the treatment groups will be compared using the Mann-Whitney U-test. Descriptive tables of IAP grade by timepoint will be presented using counts and percentages. Number of days on hemodialysis, number of days in hospital, length of stay in another health care facility and IAP value analyses will be performed for all patients and excluding deaths separately.

Complete data on organ failure free days may be unavailable due to SOFA scores not being assessed after ICU treatment. To account for this, the number of organ failure free days will be analysed by expressing these as a proportion of the days on which SOFA scores are available.

Disability measured with mRS will be summarized descriptively and the treatment groups will be compared using the Cochran-Mantel-Haenszel test for trend.

ADAs and NABs in whole blood samples up to D30 will be summarized using descriptive statistics.

All secondary analyses are designed to be supportive of the analysis of the primary endpoint and there will be no adjustments for the multiplicity of endpoints so that each analysis will be undertaken at the two-sided 5% level of significance.

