4.4.1.1 Non-attendance of Follow-up Assessments

Attempts should be made to contact patients discharged from hospital who do not attend their study follow-up assessments to ensure their well-being. In such cases, the

patient will be contacted at least twice by telephone and once by letter to request that they attend the scheduled follow-up assessment. If patients do not respond they will be considered as *lost to follow up* at that time point. If a patient is lost to follow-up, wherever possible mortality data will be sought at all remaining mortality time points from alternative sources such as the patient's local physician.

4.4.2 **Replacement Policy**

All patients who become ineligible after consenting but before randomisation are replaced and deemed as screening failures. A screening failure is defined as any patient who does not comply with the inclusion and exclusion criteria during screening **or** prior to randomisation and receiving the first dose of study medication.

Patients who complete screening and are randomised and receive at least 1 dose of the study medication will not be replaced even if later withdrawn or lost to follow up.

4.5 **Planned Sample Size and Number of Study Centres**

It is planned to randomise 152 patients at 10-18 hospital study centres in Finland, in UK, in Lithuania and in Estonia and possibly in other countries in EEA and in USA for this study. Possible additional selection will be decided later, as required. See Section 8.2. for a discussion of sample size.

4.6 **Patient Randomisation**

4.6.1 **Randomisation Scheme**

Patients are randomly assigned to treatment with FP-1201-lyo or placebo in the randomisation ratio of 2:1 (active:placebo) for treatment groups, stratified by sex and age.

The treatment assigned to each patient is determined according to a computer-generated randomisation list within eCRF.

4.6.2 **Randomisation of Patients to Treatment**

Randomisation of patients to treatment will occur immediately after completion of surgery and after all screening procedures have been performed and eligibility for inclusion in the study has been confirmed. Each randomised patient will receive a unique randomisation number. Randomised patients who terminate their study participation for any reason, regardless of whether study drug was taken or not, will retain their randomisation number.

The Investigator will use IWRS for randomisation of patients. Details can be found in the study file.

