9.1 Adjustment for covariates

The primary model will include the stratification factors (age group and gender) used in the randomisation as covariates.

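### Secondary Mann-Whitney and D90 log-rank tests name no randomisation strata: valid, but conservative to the extent that age and sex are prognostic, and the D90 p-value is not from the model giving its hazard ratio

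*SAP*

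**What the plan says.** Protocol section 4.6.1 allocates patients 2:1, "stratified by sex and age". It gives no age cut-off and no block size. SAP section 9.1 carries the strata into the primary analysis: "The primary model will include the stratification factors (age group and gender) used in the randomisation as covariates". SAP section 12.1.1 repeats this.

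SAP section 12.2 treats the secondary endpoints in three ways:

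- **Seven endpoints** (ventilator-free days, ICU-free days, organ-failure-free days, haemodialysis days, hospital days, stay in another facility, IAP): "the treatment groups will be compared using the Mann-Whitney U-test". No strata are named. Protocol section 8.5.2 names the same test for five of these; hospital days and stay elsewhere are added by the SAP.
- **D90 mortality**: a Cox model that includes the stratification factors where feasible, then "Estimated hazard ratios will be presented with associated 95% CIs and log-rank p-values for the FAS-E". The log-rank test is not said to be stratified. Protocol section 8.5.2 also pairs hazard ratios with log-rank p-values but does not adjust the hazard ratio. The covariates, and so the mismatch, enter with the SAP.
- **mRS**: "compared using the Cochran-Mantel-Haenszel test for trend", also without strata. I do not size this one.

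The secondary analyses are described as supportive, without multiplicity adjustment, and "each analysis will be undertaken at the two-sided 5% level of significance".

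**The concern.** Stratified allocation balances the arms within sex and age groups, so differences between those groups largely drop out of the treatment contrast. A test that ignores the strata still counts those differences as noise. When the strata predict outcome, its standard error is too large: it rejects less often than 5% under the null and has less power than a test using the same factors. The first interim analysis had 35 evaluable patients against 129 planned (35/129 = 27%), and the study then stopped, so avoidable losses matter.

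The D90 issue is separate. The hazard ratio and interval are adjusted for sex and age group, while the p-value beside them comes from a test that, as ordinarily run, is not. The interval can exclude 1 with p above 0.05, or the reverse, and the SAP does not say which governs.

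**Working it through.** **1. The plan's own figure.** The documents give no power or error rate for the secondary tests. The design figure they do give (SAP section 6) is 86 v 43 patients, 15% v 37%, two-sided 0.05, 80% power. Pooled rate = (43 × 0.37 + 86 × 0.15)/129 = 0.2233. Null SE = √[0.2233 × 0.7767 × (1/43 + 1/86)] = 0.0778. Alternative SE = √(0.37 × 0.63/43 + 0.15 × 0.85/86) = 0.0831. Power = Φ[(0.22 − 1.96 × 0.0778)/0.0831] = 79.2%. This reproduces.

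**2. Why size falls.** Take two equal age groups whose means differ by g within-group SDs, perfectly balanced across arms. The contrast has variance proportional to 1, but an unstratified test uses 1 + g²/4. Its effective critical value is 1.96 × √(1 + g²/4):

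| g | critical value | true size |
|---|---|---|
| 0 | 1.960 | 5.0% |
| 0.5 | 2.020 | 4.3% |
| 0.8 | 2.111 | 3.5% |
| 1.2 | 2.286 | 2.2% |

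This is a large-sample guide. With about 35 patients in four strata the balance is imperfect.

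**3. Simulation, Mann-Whitney (MW) v rank ANCOVA.** Assumptions, none in the documents: 20% female, 50% in the older group, blocks of 6 within four strata, a 0-30 day score, 4,000 trials per setting. Rank ANCOVA regresses the ranks on arm, age group and sex. The effect is 0.9 SD at n = 35 and 0.5 SD at n = 129.

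| Age-group gap (SD) | 0 | 0.5 | 0.8 | 1.2 |
|---|---|---|---|---|
| n = 35 power, MW | 64.0% | 62.5% | 57.8% | 50.2% |
| n = 35 power, rank ANCOVA | 63.7% | 65.1% | 63.5% | 63.1% |
| difference (points) | −0.3 | +2.6 | +5.7 | +12.9 |
| n = 35 size, MW | 5.1% | 3.7% | 3.6% | 3.0% |
| n = 35 size, rank ANCOVA | 5.1% | 4.5% | 4.8% | 5.4% |
| n = 129 power, MW | 74.4% | 70.0% | 66.4% | 59.1% |
| n = 129 power, rank ANCOVA | 74.3% | 72.3% | 72.3% | 72.6% |

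Monte Carlo error is √(0.6 × 0.4/4000) = 0.8 points for power and √(0.05 × 0.95/4000) = 0.3 points for size. A repeat with 15% female gave 64.0 v 63.6% at no gap, a gain of about 1 to 2 points at 0.3-0.5 SD and 6 to 13 at 0.8-1.2 SD, with MW size 2.6 to 3.5% at the larger gaps.

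**4. Van Elteren instead.** In the step 3 settings at n = 35 its power is 60.0, 60.9, 60.4 and 59.9%. It is 4.0 points below MW when the strata carry no information (64.0 − 60.0), a loss that rank ANCOVA avoids.

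**5. D90 mortality, n = 35.** Assumptions: placebo mortality 37%, hazard ratio 0.35 when there is an effect, 20% female, 50% older, blocks of 6, 6,000 trials. Age/sex hazard ratios: none (1/1), moderate (2/1.3), strong (4/2).

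| Prognostic effect | none | moderate | strong |
|---|---|---|---|
| size, log-rank → stratified | 5.0 → 5.0% | 4.3 → 4.7% | 3.5 → 4.8% |
| power, log-rank → stratified | 34.8 → 33.4% | 33.8 → 33.2% | 29.3 → 32.2% |
| log-rank and adjusted Cox differ at 0.05, null | 1.9% | 2.2% | 2.8% |
| same, with effect | 5.0% | 6.2% | 6.7% |
| adjusted Cox not fitted, null / effect | 6.7 / 22.2% | 5.1 / 20.1% | 5.2 / 22.8% |

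Some disagreement appears even with no prognostic effect, because the two tests are different procedures. At n = 129 the rate is 0.7 to 4.9%.

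**The case against.** The best reply is that this is a conditional efficiency argument about valid tests on supportive endpoints. Most of its premises stand:

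- No simulated setting inflates type I error. The primary analysis is adjusted, and D90 mortality also gets a logistic regression like the primary one.
- The documents give no prognostic effect for age or sex. A separate check with a continuous age effect of 0, 0.2 and 0.3 SD per SD of age gave MW v rank ANCOVA power of 65.0 v 64.9%, 61.3 v 63.0% and 60.4 v 63.6%. The gain is 0 to 3 points unless age is strongly prognostic.
- In that check MW size was already 4.1% with no age effect, using the normal approximation with continuity correction. Not every shortfall below 5% comes from the strata.
- The SAP is silent rather than prescribing unstratified tests, and it allows for the adjusted Cox model not being feasible. If the covariates are dropped, hazard ratio and log-rank p-value are both unadjusted and the mismatch in adjustment goes.
- This SAP version postdates the interim analysis, so replacing a protocol-named test now is itself a departure.

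These points limit the size of the concern without removing it. A Mann-Whitney test is run without strata unless someone says otherwise, and rank ANCOVA costs nothing measurable when the strata are uninformative. The D90 mismatch follows from the wording whenever the adjusted model is fitted.

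**Conclusion.** The point holds in a conditional form and is modest. The secondary tests ignore the randomisation strata where the primary model uses them. At about 35 patients the cost is 0 to 3 power points for weak to moderate prognostic effects and 6 to 13 for strong ones, with MW size about 2.6 to 3.5% in the strong cases. The D90 p-value and the adjusted hazard ratio disagree at 0.05 in roughly 2 to 7% of trials. All of these figures rest on the assumed strata, distributions and effects in the working. The final number analysed is taken as about 35.

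A reader might infer three stronger things that the documents do not support:

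- **That the tests are conservative and underpowered as such.** With no prognostic effect, neither is true.
- **That stratifying always helps.** Van Elteren and the stratified log-rank can lose power at this size; the log-rank loses 1.4 points (34.8 − 33.4) when the strata carry no information.
- **That D90 contradictions would be frequent.** A rate of 8 to 10% among estimable trials arose under other assumptions (D90 mortality 42% v 20%, age log-hazard ratio 1.1 or 1.6). The settings above did not reproduce it, and I do not rely on it.

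**What to change.** In SAP section 12.2:

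- For the seven endpoints now tested by Mann-Whitney, make the main comparison a rank ANCOVA (ranks regressed on arm, age group and sex). Keep the plain Mann-Whitney as a sensitivity result.
- For D90 mortality, take the p-value from the same Cox model as the hazard ratio and interval. If the adjusted model is not feasible, report the unadjusted hazard ratio with the unstratified log-rank p-value, so that estimate and p-value always carry the same adjustment. State in advance what counts as not feasible; the failure rates in step 5 show that the fallback may be needed.

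In SAP section 15, list both changes as deviations from the protocol made after the interim analysis.

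The cost is a few lines of text and code and a small, declared departure from the protocol-named tests at a late stage. Rank ANCOVA has no power cost beyond simulation error when the strata are not prognostic. In the fallback, a Wald interval and a log-rank p-value can still differ narrowly around 0.05, so the SAP should say which is read first.
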